## 1.5. Sample Size Justification

There is no established standard of care for the targeted population, and the recent approvals were based on single-arm studies with ORR as the primary endpoint. In a previous clinical study (MMY2002), of 106 subjects with relapsed or refractory multiple myeloma who had received at least 3 prior therapies and who were treated with Dara IV 16 mg/kg, an ORR of 29.2% (95% CI: 20.8%, 38.9%) was observed.

Non-inferiority of Dara SC to Dara IV in the current study is defined using a 60% retention of the lower bound (20.8%) of the 95% CI from Study MMY2002. The clinical relevance of the 60% retention of ORR was justified based on the benefit/risk of Dara SC and a strong indication of similar efficacy from early efficacy and pharmacokinetics data. The 60% retention will result in minimal loss of benefit in terms of observed ORR.

With a planned 1:1 randomization, 480 subjects (n=240 in the Dara SC group and n=240 in the Dara IV group) will be needed to demonstrate non-inferiority with a power of 80% and a one-sided  $\alpha=0.025$ , assuming that the true ORR is the same for both groups. The sample size calculation is based on the methodology for the non-inferiority test for non-unity null, as described by Farrington and Manning (1990).

The study is also designed to establish comparability of maximum  $C_{\text{trough}}$  between Dara SC and Dara IV. The 2 formulations of daratumumab will be considered similar if the lower bound of the 90% CI for the ratio of the geometric means of  $C_{\text{trough}}$  on Cycle 3 Day 1 is at least 80% (non-inferiority margin of 20%). A one-sided test is selected based on previous analyses that demonstrated a strong relationship between maximum  $C_{\text{trough}}$  and efficacy. However, there is no apparent relationship between drug exposure in the therapeutic dose range and adverse events of interest. With a planned 1:1 randomization, 480 subjects and a one-sided  $\alpha=0.05$ , the power will be >95%. This assumes a true ratio of the  $C_{\text{trough}}$  of 1, a non-inferiority margin of at least 80% of the geometric mean ratio, a coefficient of variation of 0.6.

## 1.6. Randomization and Blinding

Central randomization will be implemented in this study. Subjects will be assigned randomly to 1 of 2 treatment groups based on a computer-generated randomization schedule prepared before the study by or under the supervision of the sponsor. The randomization will be balanced by using randomly permuted blocks and will be stratified by body weight at baseline ( $\leq 65$  kg, 66 kg to 85 kg,  $> 85$  kg), number of prior lines of therapy ( $\leq 4$  prior lines versus  $> 4$  prior lines), and type of myeloma (IgG versus non-IgG). An interactive web response system (IWRS) will assign a unique treatment code, which will dictate the treatment assignment and matching study drug kit for the subject.

As this is an open-label study, blinding procedures are not applicable.

## **2. GENERAL ANALYSIS DEFINITIONS**

### **2.1. Visit Windows**

For analyses of data by cycle, if data are collected by date (e.g., AE onset), the corresponding study evaluations will be assigned to actual sequential cycles, which are derived from the study drug administration data. The start date of a cycle is defined as the first scheduled dose date of the study drug for that particular cycle, and the end date of a cycle is the start date of the next cycle minus 1. For the last cycle, the end date is defined as the end of treatment visit date or the minimum of last dose date plus 30 days or subsequent anticancer therapy minus 1 day, if the end of treatment visit date is not available.

In general, if data (e.g., laboratory and vital sign etc.) are collected by cycle, the nominal cycle will be used to summarize data. However, due to possible cycle delays, assessment performed in the same cycle may not be well aligned in time scale for different subjects. To address this, by-week windowing rules may be applied in the overtime data summary by study week.

### **2.2. Pooling Algorithm for Analysis Centers**

Data from all study centers will be pooled for analyses.

### **2.3. Study Drug**

In this study, study drug refers to Dara SC or Dara IV. In the Dara SC group, Dara SC will be administered by SC injection at a fixed dose of 1800 mg. In the Dara IV group, Dara IV 16 mg/kg will be administered by IV infusion. Each subject's dose in the Dara IV group will be calculated based on the subject's weight rounded to the nearest kilogram, but does not need to be recalculated for weight changes that are <10% from baseline.

Dose reduction or increase of Dara IV or Dara SC is not permitted. Dose delay or dose skip is the primary method for managing daratumumab-related toxicities.

The first dose date is defined as the earliest date of non-zero dose of study drug. The last dose date is defined as the latest date of non-zero dose of study drug.

A subject is considered as treated in a cycle if he/she receives any non-zero dose of study drug in that cycle.

### **2.4. Baseline Definitions**

The baseline value is defined as the last non-missing measurement taken on or prior to the first dose administration of study drug (including time if time is available).

Study day is defined as date of assessment – first dosing date + 1 for any assessment done on or after first dosing date; otherwise, study day is defined as date of assessment – first dosing date. The first dose date is defined as the earliest date of non-zero dose of study drug.

## 2.5. Unique Lab Value

In general, in instances when there are multiple records at a given visit date for lab parameters associated with disease assessment, the following rules will be applied to select the unique lab value for analysis: a.) multiple records from both central and local lab, central lab value always takes precedence over local lab value; b) multiple records from central lab, select the latest value as the unique lab value; c.) multiple records from local lab, select the latest lab value as the unique lab value.

## 2.6. Analysis Sets

The analysis sets for the study are:

- Intent-to-treat (ITT) analysis set: defined as all subjects randomized into the study. This analysis set will be used for summary of study populations, analyses of disposition, demographic, baseline disease characteristics, and analyses of efficacy endpoints including time-to-event endpoints. All subjects in ITT analysis set will be analyzed according to their randomized treatment group, regardless of the actual treatment received.
- Safety analysis set: defined as all randomized subjects who receive at least 1 dose of study drug (Dara SC or Dara IV). This analysis set will be used for all safety analyses and analyses of exposure. All subjects in safety analysis set will be analyzed according to the actual treatment that they received.
- Per-protocol (PP) analysis set: defined as all treated subjects who have measurable disease at baseline and have no major protocol deviations with respect to eligibility. The per-protocol analysis set will be used for critical sensitivity analyses of ORR in the context of the non-inferiority design.
- Response-evaluable analysis set: defined as subjects who have a confirmed diagnosis of multiple myeloma and measurable disease at baseline or screening visit. In addition, subjects must have received at least 1 administration of study drug and have at least 1 post baseline disease assessment. Measurable disease at baseline is defined in section 2.9.1. This analysis set will be used as sensitivity analyses for selective response-related endpoints such as ORR, VGPR or better rate, and CR or better rate.
- Pharmacokinetics analysis set: defined as subjects who received at least 1 administration of study drug and have at least 1 pharmacokinetics sample concentration value after the first dose administration. All pharmacokinetic parameters except for maximum  $C_{\text{trough}}$  will be analyzed based on the pharmacokinetics analysis set.
- Pharmacokinetics-evaluable analysis set: defined as subjects who received all 8 weekly full doses of Dara IV or Dara SC in Cycle 1 and Cycle 2 within the dosing time window according to the Time and Events Schedule in protocol and provided a pre-dose pharmacokinetic sample on Cycle 3 Day 1 within the sampling window of 8 hours prior to

the start of dose administration. The Pharmacokinetics-evaluable analysis set will be used to summarize the maximum  $C_{\text{trough}}$ .

- Immunogenicity-evaluable analysis set:
  - Daratumumab immunogenicity-evaluable: Immunogenicity-evaluable analysis set for antibodies to daratumumab is defined as all subjects who receive at least 1 dose of Dara SC or Dara IV and have appropriate serum samples for detection of anti-daratumumab antibodies to daratumumab (at least 1 sample after the start of the first dose of daratumumab).
  - rHuPH20 immunogenicity-evaluable: Immunogenicity-evaluable analysis set for anti-rHuPH20 antibodies is defined as all subjects who receive at least 1 dose of Dara SC and have appropriate plasma samples for detection of antibodies to rHuPH20 (at least 1 sample after the start of the first dose of Dara SC).

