9.7 Safety Evaluations	Subjects who are positive for antiHBc or antiHBs will undergo testing for hepatitis B DNA by PCR every 4 weeks (each cycle). Subjects who are positive for antiHBs antibodies due to prior immunization are not required to be monitored by HBV DNA by PCR. During and following study treatment, subjects who have history of HBV infection will be closely monitored for clinical and laboratory signs of reactivation of HBV according to the JSH Guidelines for Prevention of HBV reactivation in patients receiving Immunosuppressive Therapy or Chemotherapy (JSH Guidelines for the Management of Hepatitis B Virus Infection ⁷). Where required by local law, the result of HBV testing may be reported to the local health authorities.
Attachment 4: Modified Diet in Renal Disease Formula	An error in the modified diet in renal disease formula calculation has been corrected.
Rationale: Updated Attachment 10 to include SEBIA Hydrashift 2/4 Daratumumab IFE Interference assay.	

Applicable Section(s)	Description of Change(s)
Updated Attachment 10: Interpretation of the SEBIA Hydrashift 2/4 Daratumumab IFE Interference Assay	Text updated to delete reference to the DIRA assay and include the three outcomes of the SEBIA Hydrashift 2/4 Daratumumab IFE Interference assay.
Rationale: Minor changes made to the protocol.	
4.3 Prohibitions and Restrictions; 8.3 Prohibited Therapies	The following text related to IV contrast being used in CT in subjects with multiple myeloma has been deleted from the protocol. Typically, IV contrast is not used in computed tomography (CT) scanning of subjects with secretory multiple myeloma because of the risk to the kidney. If administration of IV contrast is necessary, then adequate precautions including hydration are indicated.
4.2 Exclusion Criteria, Criterion #5.2; 4.2 Exclusion Criteria, Criterion #8.2; 6.2.2 Intravenous Administration, Table 4; 6.3.1 Predose medications; 6.3.2 Postdose medications;	Minor editorial and grammatical changes made to the text of the protocol for clarifications.

Amendment 1 (7 December 2017)

This amendment is considered to be substantial based on the criteria set forth in Article 10(a) of Directive 2001/20/EC of the European Parliament and the Council of the European Union.

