Rationale: Correction of methodology for bone marrow testing	
Time and Event Schedule, Table 1, Bone marrow aspirate/biopsy;	Added text to table to indicate that FISH was the preferred method of testing and to clarify that if a fresh aspirate bone marrow sample was obtained, a portion was to be sent to the central lab for biomarker evaluation; DNA/RNA sequencing replaced with biomarker evaluation. A typographical error “and phenotyping” was corrected to read “or karyotyping”.
9.2.5. Bone Marrow Examination, Table 7	Text “Cytogenetics by FISH (preferred) or karyotyping” added under Local Testing. Text under Central Testing revised to indicate that if a fresh bone marrow aspirate is collected at Screening, a portion will be sent to a central laboratory for biomarker evaluation; DNA/RNA sequencing replaced with biomarker evaluation.
Rationale: To provide operational flexibility for study sites, MRI added as an option for skeletal survey.	
Time and Event Schedule, Table 1, Skeletal survey	Added text that x-ray or MRI may be used as alternatives for skeletal surveys if applicable in local practice.
Rationale: Corrections and clarifications for PK sample collection.	
Time and Event Schedule, Table 2	
PK sample collection windows on dosing days changed from ± 1 day or ± 3 days (depending on cycle) to ± 0 days. Footnote “a” modified to indicate that samples collected on dosing days must be collected on the day of study drug administration. Text indicating collection of samples ± 4 hours of the time of study drug administration on non-dosing days deleted.
 
Samples obtained at non-dosing days Cycle 1 Day 4, Cycle 3 Day 4, Follow-up post-treatment Week 4 and Follow-up post-treatment Week 8 moved to “After dose” line in table for clarity.
 
New footnote “c” added that end of dose samples (Dara-IV) should be collected after the end of infusion (up to 2 hours after the end of infusion).

Rationale: Inclusion criterion for measurable disease revised to align with current IMWG criteria	

Applicable Section(s)	Description of Change(s)
4.1. Inclusion Criteria 2	Text revised to define documented multiple myeloma as serum M-protein level ≥ 1.0 g/dL or urine M-protein level ≥ 200 mg/24 hours. Text defining measurable disease for IgA, IgD, IgE, and IgM multiple myeloma as serum M-protein level ≥ 0.5 g/dL or urine M-protein level ≥ 200 mg/24 hours deleted.
Rationale: Exclusion criteria revised to align with ASCO recommendations	

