4.1. Inclusion Criteria

Each potential subject must satisfy all of the following criteria to be enrolled in the study:

1. At least 18 years of age.
2. Criterion updated as per Amendment 1
 - 2.1. Documented multiple myeloma as defined by the criteria below:
 - Multiple myeloma diagnosis according to the IMWG diagnostic criteria (refer to [Attachment 1](#)).
 - Measurable disease at Screening as defined by any of the following:
 - Serum M-protein level ≥ 1.0 g/dL or urine M-protein level ≥ 200 mg/24 hours; or
 - Light chain multiple myeloma without measurable disease in the serum or the urine: Serum immunoglobulin FLC ≥ 10 mg/dL and abnormal serum immunoglobulin kappa lambda FLC ratio.
3. Evidence of a response (PR or better based on investigator's determination of response by IMWG criteria) to at least 1 prior treatment regimen.
4. Relapsed or refractory disease as defined below:
 - Relapsed disease is defined as an initial response to previous treatment, followed by confirmed PD by IMWG criteria >60 days after cessation of treatment.
 - Refractory disease is defined as $<25\%$ reduction in M-protein or confirmed PD by IMWG criteria during previous treatment or ≤ 60 days after cessation of treatment.

5. Received at least 3 prior lines of therapy (refer to [Attachment 2](#)) including a PI (≥ 2 cycles or 2 months of treatment) and an IMiD (≥ 2 cycles or 2 months of treatment) in any order during the course of treatment (except for subjects who discontinued either of these treatments due to a severe allergic reaction within the first 2 cycles/months). A single line of therapy may consist of 1 or more agents, and may include induction, hematopoietic stem cell transplantation, and maintenance therapy. Radiotherapy, bisphosphonate, or a single short course of corticosteroids (no more than the equivalent of dexamethasone 40 mg/day for 4 days) would not be considered prior lines of therapy.

or

Refractory to both a PI and an IMiD. For subjects who have received more than 1 type of PI, their disease must be refractory to the most recent one. Similarly, for those who have received more than 1 type of IMiD, their disease must be refractory to the most recent one.

6. ECOG Performance Status score of 0, 1, or 2 (refer to [Attachment 3](#)).
7. Pretreatment clinical laboratory values meeting the following criteria during the Screening Phase:

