**AMENDMENT HISTORY**

SAP Version	Issue Date
Original SAP	6 February 2018
Amendment 1	12 February 2019

The following is a summary of the major changes from the original version of the SAP:

1. Updates on the data cutoff and primary analysis strategy according to the Protocol Amendment 2 to allow Japan to enroll beyond the initially planned 480 subjects;
2. Updated and clarified on the Statistical Hypotheses Section 1.3 and Efficacy Section 5, added a new Section 1.4 of Non-inferiority Margins Justification to address FDA's comments on alpha level, estimand and non-inferiority margins;
3. Refined the parameters for the biomarker analysis;
4. Added exploratory endpoint and analyses for PFS2 (Section 5.4.2);
5. Added attachments of IMWG computerized algorithm and additional exploratory analysis to support HEMAR.

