## 2.9. Other General Definitions

### 2.9.1. Measurable Disease of Multiple Myeloma at Baseline and Measurable Type

Measurable disease at baseline is defined by any of the following:

- IgG multiple myeloma: Serum M-protein level  $\geq 1.0$  g/dL or urine M-protein level  $\geq 200$  mg/24 hours; or
- IgA, IgD, IgE, IgM multiple myeloma: serum M-protein level  $\geq 0.5$  g/dL or urine M-protein level  $\geq 200$  mg/24 hours; or
- Light chain multiple myeloma without measurable disease in the serum or the urine: Serum immunoglobulin free light chain (FLC)  $\geq 10$  mg/dL and abnormal serum immunoglobulin kappa lambda FLC ratio.

If a subject meets the criteria for serum M-protein, the measurable disease type is serum; otherwise, if a subject meets the criteria for urine M-protein, the measurable disease type is urine; otherwise if a subject meets the criteria for FLC, the measurable disease type is FLC. If a subject meets both of the criteria for serum M-protein and urine M-protein, then the measurable disease type is “serum and urine”.

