### 5.1.2. Computerized Algorithm

A validated computerized algorithm (Attachment 2), which is based on the IMWG response criteria (Durie 2006, Rajkumar 2011) and has been used and validated by an independent review committee in study MMY2002, also used in MMY3003, MMY3004, MMY3007, and MMY3008 will be used to determine response and disease progression for each subject. Unless specified otherwise, relapse from CR by positive immunofixation or trace amount (defined as less than 0.5 g/dl) of M protein is not considered to be progressive disease in the IMWG response criteria.

The primary efficacy analyses will be based on the computerized algorithm assessments. Analyses for the primary endpoint ORR and selected major secondary efficacy endpoints based on investigator assessments using the IMWG response criteria will also be performed as sensitivity analyses.

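### SAP 2.9.1 keeps a 0.5 g/dL measurable-disease threshold for non-IgG heavy-chain myeloma that the protocol's inclusion criterion no longer has; sensitivity sets and M-protein outputs are affected, the primary ORR is not

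*SAP*

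**What the plan says.** SAP 2.9.1 sets the serum threshold by heavy chain. IgG disease needs 1.0 g/dL. The next line reads "IgA, IgD, IgE, IgM multiple myeloma: serum M-protein level" of at least 0.5 g/dL. Urine M-protein of at least 200 mg/24 h qualifies in either case, and there is a free-light-chain rule for light-chain disease.

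Protocol 4.1, criterion 2.1, begins "Measurable disease at Screening as defined by any of the following". It then gives 1.0 g/dL in serum or 200 mg/24 h in urine with no exception by heavy chain, plus the same light-chain rule.

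SAP 2.6 uses the term in two sets:

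- **Response-evaluable set.** It supports sensitivity analyses of ORR, VGPR or better and CR or better. It accepts measurable disease at baseline or the screening visit, and it points to the definition: "Measurable disease at baseline is defined in section 2.9.1".
- **PP set.** It is "defined as all treated subjects who have measurable disease at baseline and have no major protocol deviations with respect to eligibility". Protocol 11.1 defines it the same way. Both documents call it critical for checking ORR in the non-inferiority design.

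SAP 2.4 defines baseline as the last value on or before the first dose. SAP 5.2.3 makes ITT the primary ORR set.

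**The concern.** The two current texts disagree on who has measurable disease. The protocol's log for Amendment 1, dated 7 December 2017, shows where the 0.5 g/dL figure came from: it lists as deleted the "Text defining measurable disease for IgA, IgD, IgE, and IgM multiple myeloma as serum M-protein level" of at least 0.5 g/dL. The log is not needed to find the conflict; it only explains it. The first SAP is dated 6 February 2018 and the current one "12 February 2019", 61 and 432 days after that amendment. Neither says why the old figure stays.

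Programmed as written, the response-evaluable ORR can include subjects whose disease is not measurable under the current protocol. So can the PP ORR, for some subjects. Measurable-disease type and best M-protein response follow the same definition.

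A separate and lesser matter is what the PP set can show. Among major deviators it removes only those who deviated on eligibility. SAP 4.8 also lists subjects given the wrong treatment or dose, and subjects given a disallowed therapy. None of the five ORR analyses in SAP 5.2.3 (ITT, PP, response-evaluable, investigator-assessed, first 480 randomized) leaves them out. Agreement of PP with ITT therefore says nothing about deviations of that kind.

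**Working it through.** **1. The plan's own figure.** Inputs from Protocol 11.2: ORR 20.8% in both arms, RR margin 0.60, one-sided alpha 0.025, 240 per arm. The Farrington-Manning restricted null rates are 0.1535 (SC) and 0.2559 (IV).

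- Null SE = √[(0.1535×0.8465 + 0.36×0.2559×0.7441)/240] = 0.02876
- Alternative SE = √[0.208×0.792×1.36/240] = 0.03055
- Power = Φ[(0.4×0.208 − 1.96×0.02876)/0.03055] = Φ(0.878) = 81.0%

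Eighty percent power needs 234 per arm, 468 in all, so 480 reproduces. Nothing below disputes it.

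**2. Who is affected.** The band is non-IgG heavy-chain disease with serum M-protein from 0.5 to below 1.0 g/dL.

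| Output | Effect of the 0.5 g/dL rule |
|---|---|
| ITT ORR (primary) | None; all randomized subjects are included |
| Response-evaluable set | Band subjects with urine below 200 mg/24 h are included; there is no filter on eligibility deviations |
| PP set | Band subjects at baseline with urine below 200 mg/24 h are included if they are not major eligibility deviators |
| Measurable type (2.9.1, 4.2) | A band subject with urine of 200 mg/24 h or more is typed as serum and urine, not urine |
| Best M-protein response (5.4.1) | For that subject it is read from serum, not urine |

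Two kinds of subject can be in the PP band without an eligibility deviation. One was enrolled under the original 0.5 g/dL rule. The other had, say, 1.0 g/dL at Screening and 0.9 g/dL at Cycle 1 Day 1. Table 1 of the protocol schedules SPEP at that visit, though Protocol 9.1.2 does not make the repeat mandatory. This subject is eligible, but the baseline value is in the band.

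**3. Size.** The documents give no count, so the share s of an arm in the band is assumed. If s is the same in both arms and q is the response rate within the band, removing the band gives

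RR = (ORR_SC − s·q_SC)/(ORR_IV − s·q_IV),

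because the factor 1 − s cancels. If band subjects respond like the rest of their arm, the RR does not move. A small example at ORR 20.8%: 240 × 0.208 ≈ 50 responders per arm, and s = 2% is about 5 subjects. If 2 of 5 respond on SC and 1 of 5 on IV, the RR goes from 1.00 to 48/49 = 0.98.

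The logical limits at equal ORR of 20.8% have every band subject responding in one arm and none in the other:

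- s = 1%: 0.198/0.208 = 0.95 to 0.208/0.198 = 1.05
- s = 2%: 0.188/0.208 = 0.90 to 0.208/0.188 = 1.11
- s = 5%: 0.158/0.208 = 0.76 to 0.208/0.158 = 1.32

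For a single arm the limits are (ORR − s)/(1 − s) to ORR/(1 − s). For ORR 20.8% and s = 1, 2, 5% these are 20.0–21.0%, 19.2–21.2% and 16.6–21.9%.

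**4. The optional table.** These figures come from exact enumeration: binomial probabilities summed over every pair of responder counts that the Farrington-Manning test rejects. They are for ORR alone, at IV ORR 20.8% / 29.2%. The deviation pattern is assumed: 12 of 240 SC subjects are excluded from the supportive set.

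- False non-inferiority at true RR 0.60 with no deviations: 2.6% / 2.6%.
- The same if the 12 respond at the IV rate: 3.7% / 4.0%. Excluding them reverses 32% / 37% of those false passes.
- If the 12 respond like other SC subjects, excluding them still reverses 15% / 16% of false passes.
- ITT passes and the supportive analysis fails in 1.2% / 1.5% of trials at RR 0.60 (12 responding as IV), and in 2.5% / 1.2% at RR 1.0.
- Power at equal ORR with 240, 228 and 216 per arm: 81, 79 and 77% at 20.8%; 94, 93 and 92% at 29.2%. The formula in step 1 agrees to within half a point.

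**The case against.** An enrollment rule applied at Screening and an analysis definition applied at baseline need not be identical. The 0.5 g/dL line may be there on purpose, for subjects properly enrolled before Amendment 1 took effect at their site. Protocol 17.1 ties implementation to ethics approval, so the 61-day gap by itself proves little. Subjects enrolled under the current rule with a band value at Screening are eligibility deviators, and the PP set already drops the major ones. Randomization is stratified by IgG versus non-IgG, which limits arm imbalance in the group these subjects come from.

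Most of this stands, and it is why the effect is likely to be small. It does not remove the conflict. SAP 2.9.1 applies 0.5 g/dL to everyone without stating a reason, and the response-evaluable set has no eligibility filter. The Screening-versus-baseline point also shows that changing the threshold alone would drop eligible subjects from the PP set.

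On the PP definition the objection is stronger. Protocol and SAP agree, so there is no contradiction. SAP 5.2.1 already refuses to count responses reached after subsequent anticancer therapy. The added table would detect little: nearly half of the 32–37% reversal appears even when the excluded subjects have no deviation effect.

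A reader might go further and infer three things that the documents do not support:

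- **That the primary non-inferiority result is compromised.** It is not; it uses ITT.
- **That the response algorithm carries the 0.5 g/dL rule.** SAP Attachment 2 is not in the available text, so nothing can be said.
- **That SAP 5.1.2 shows a band value is too small to measure.** Its statement that a "trace amount (defined as less than 0.5 g/dl) of M protein is not considered to be progressive disease" concerns relapse from CR, not measurability.

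**Conclusion.** The threshold conflict is real and should be corrected. It is confined to two sensitivity sets (the response-evaluable set, and the PP set for the two groups named above), measurable-disease type, and best M-protein response. Primary ORR, sample size, alpha and primary power do not change. The count is unknown and the effect on the RR is probably small. That judgement assumes few subjects in the band and similar response there in both arms; the wide limits at 5% need complete separation of the arms.

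The narrow PP exclusion is not an error. A further supportive table is optional. The false-pass rates behind it rest on assumed deviation rates and responses, and because the overall claim also needs maximum Ctrough they are upper limits for that claim.

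**What to change.** **Correction.**

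- Align the serum threshold in SAP 2.9.1 with inclusion criterion 2.1.
- In both the PP and the response-evaluable set, accept measurable disease at Screening or baseline, so that eligible subjects are not lost.
- Flag subjects enrolled under the original 0.5 g/dL rule. Report the RR and 95% CI for PP and response-evaluable ORR with and without them.
- Re-derive measurable type and best M-protein response.
- If the 0.5 g/dL rule was kept deliberately for those subjects, limit it to them in 2.9.1 and still report both ways.

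The cost is SAP wording, a matching clarification of the PP set in Protocol 11.1, and re-derivation of the two sets and the M-protein outputs.

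**Optional addition.** Keep ITT as the decision analysis and keep the present PP analysis. Add one supportive ORR table that also excludes major SAP 4.8 deviations for wrong treatment or dose, or for disallowed therapy with anti-myeloma activity, within a window fixed in advance and the same for all subjects. Fix the list of excluded subjects before ORR is analyzed by arm. Show the RR and 95% CI beside ITT, without a pass/fail reading; disagreement should prompt a look at the excluded subjects.

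The cost is one table from deviation data already collected. Power is slightly lower (81% to 79% at 228 per arm, ORR 20.8%), detection is weak, and exclusion after randomization in an open-label trial can cause selection bias.
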